**Table II (continuation): Patient follow-up variables**

Variables	Unit of measurement	Type
Functional Capacity and Pain (Oxford Hip Score)	Points (0 to 48)	Quantitative and Qualitative
Falls Risk (STRATIFY Scale)	Points (0 to 5)	Quantitative and Qualitative
Medical complications	0= Fall. 1= Pneumonia. 2= New fractures. 3= Dementia. 4= Acute Myocardial Infarction 5= Pulmonary embolism. 6=Deep vein thrombosis; 7=Death.	Qualitative
Quality of life analysis: questionnaire EQ-5D-5L	Levels (1 to 3125) Points (0 to 100)	Qualitative Quantitative
Abbreviations: RNFC: National Hip Fracture Registry, mFAC: Modified Functional Ambulatory Classificator,		

- **Level of dependency: the Spanish version of the *Barthel Index* will be used (Annex I).** The "*Barthel Index*" provides quantitative information on the level of dependence for activities of daily living by measuring ten activities that are considered basic (441,42). This scale has been used in other studies and shows a direct relationship between high levels of dependency and poor physical health (441). "The Barthel Index has demonstrated good inter-observer reliability, with Kappa indices between 0.47 and 1.00, intra-observer reliability with a Kappa index between 0.84 and 0.97 and internal consistency with a Cronbach's alpha of 0.86-0.92 (39-41).

Test results:

- Values: 0-20 total dependency.
- Values: 21-60 severe dependence.

- Values: 61-90 moderate dependence.
- Values: 91-99 low dependency
- Values: 100 independence.

This scale is administered at 6 weeks, 4 months and 1 year.

- **Sarcopenia assessment: using the SARC-F scale (ANNEX II) (42).**

It is an easily accessible questionnaire, validated in Spanish, which allows the identification of subjects at risk of sarcopenia. The maximum score is 10 points. A score of < 4 points after the test indicates an acceptable state of health, while any score higher than this indicates a risk of sarcopenia (43).

This scale is administered at 6 weeks, 4 months and 1 year.

- **Assessment of functional capacity and specific hip pain: "Oxford Hip Score (OHS)" (ANNEX III)**

It has high repeatability and reliability, with a Cronbach's Alpha value of 0.84 preoperatively, ICC=0.94, and 0.89 at six months and one year (44).

It is a 12-item questionnaire, each item is answered on a five-level Likert-type scale where 4 is the minimum impact and 0 the most unfavourable (45).

Results:

0-19: Severe impact.

20-29: Moderate to severe impact.

30-39: Mild to moderate impact.

40-48: Satisfactory condition.

This scale is administered at 1, 3, 6 and 12 months.

- **Monitoring of adverse events.**

During the follow-up period, information will be collected on variables derived from post-surgical and medical complications, and falls risk monitoring will be performed.

- **Adverse events. Catalogued in:**

0= Fall.

- 1= Pneumonia.
- 2= New fractures.
- 3= Dementia.
- 4= Acute Myocardial Infarction.
- 5= Pulmonary embolism.
- 6=Deep vein thrombosis.
- 7= Death.

This scale is administered at 6 weeks, 4 months and 1 year.

- **Falls risk scale: STRATIFY scale.**

It can predict which patients are at high risk of falls, with sensitivity values of 92% and specificity of 68% for the elderly population (46).

The total score of the STRATIFY scale is obtained based on the sum of the answers to the five questions, which can take values between zero and five. A score of 0 corresponds to a risk considered low, equal to 1 corresponds to a moderate risk and, finally, greater than or equal to 2 corresponds to a high risk (47).

Question:

1. Patient hospitalised for falls or with episodes of falls during hospitalisation?
2. Restless patient?
3. Are you a patient with visual impairment that affects your daily activity?
4. Patient with a frequent need to use the toilet?
5. Does the patient have a transfer or mobility score of 3 or 4?

However, in the last question, the score is obtained by combining two answers from the modified Barthel index in relation to, respectively, the patient's ability to:

- Transferring from bed to a chair
  - 0: incapable.
  - 1: needs significant assistance.
  - 2: Needs minimal assistance.

3: Independent.

- Level of mobility of the patient:

0: Immobile.

1: Independent with the help of a wheelchair.

2: Use walking aids or walk with the help of a person.

3: Independent.

This scale is administered at 6 weeks, 4 months and 1 year.

- **Quality of life analysis: EQ-5D-5L questionnaire (ANNEX IV) (48).**

It is a self-administered questionnaire divided into two parts, the descriptive system and the Visual Analogue Scale (VAS).

- The descriptive system EQ-5D-5L. describes health status along five dimensions:
  - Mobility.
  - Self-care.
  - Daily activities.
  - Pain/discomfort.
  - Anxiety/depression.

Each of these dimensions has five possible responses or severity levels: no problems (1), mild problems (2), moderate problems (3), severe problems (4) and extreme problems/impossibility (5). The participant should indicate the level that best reflects his/her status for each of the dimensions, describing his/her status using five digits with values ranging from 1 to 5, with the best health status being 11111 and the worst 55555.

The combination of these levels defines a total of 3125 () health states.

- The Visual Analogue Scale (VAS). Assessment by means of a 20 cm millimetre scale in a vertical position. At the top of the scale is the message "the best state of health you can imagine" with a value of 100, at the bottom the message "the worst state of health you can imagine" with a value of 0.

This scale is administered at 1, 3, 6 and 12 months.

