### Specific objectives

- To describe the improvement in gait ability in patients undergoing hip surgery after a functional recovery programme compared to the historical control group (exposed cohort).
- To describe the clinical and functional characteristics of the patients operated on for hip fracture in the SJD hospital in León who are being followed up by the new system of care implemented in comparison with the historical control group (exposed cohort).
- To analyse risk and protective factors related to the level of dependency and mortality at 30 days and one year of follow-up in patients operated on for hip fracture at the SJD hospital in León.
- To describe the impact of a functional recovery programme on the prevention and treatment of sarcopenia in the new unexposed cohort.
- To describe the quality of life and patient-reported outcomes in the new unexposed cohort.
- To analyse the impact of a functional recovery programme on the prevention of falls in elderly patients who have undergone hip fracture surgery.

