**Table III. Summary of variables, assessment instruments and collection period**

Variable	Questionnaire	Time of administration
March Capacity	RNFC scale	Entry, at 6 weeks, 4 months and 1 year.
	The walking capacity assessment scale (mFAC).	Entry, at 6 weeks, 4 months and 1 year.
Physical capacity	Barthel Index	At 6 weeks, 4 months and 1 year.
	Oxford Hip Score Scale	At the 1st, 3rd, 6th and 12th month.
Sarcopenia	SARC-F Scale	At 6 weeks, 4 months and 1 year.
Adverse Events	STRATIFY scale	At 6 weeks, 4 months and 1 year.
	Medical complications (ad hoc questionnaires)	At 6 weeks, 4 months and 1 year.
Quality of life	Questionnaire EQ-5D-5L	At the 1st, 3rd, 6th and 12th month.

- The functional recovery programme designed and implemented as standard practice from 1 January 2021. This programme consists of a series of presentations and videos, in simple language with information and recommendations. It will provide answers to patients' most frequently asked questions and will also allow patients to receive reminders regarding their care (recommended exercises, precautions to take in certain circumstances, alerts, etc.).

It is the clinician and the patient, or family member if applicable, who enters the data directly into the application, prior to accepting the legal clauses to that effect.

The study variables collected in the project are included among the clinical variables included in the orthogeriatric protocol for the care of hip fracture patients at the HSJD. In order to analyse those established for this study, the variables will be extracted from the data collection platform, the PI being responsible for the storage and processing of the data in accordance with current legislation.

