**Annex II: SARC-F Questionnaire (Spanish version) for the assessment of sarcopenia.**

**SARC-F Questionnaire**

Date :

Name :

Test administered by :

Component	Question	Scoring	Score
Strength	How much difficulty do you have in lifting and carrying 10 pounds?	None = 0 Some = 1 A lot or unable = 2	
Assistance in walking	How much difficulty do you have walking across a room?	None = 0 Some = 1 A lot, use aids, or unable = 2	
Rise from a chair	How much difficulty do you have transferring from a chair or bed?	None = 0 Some = 1 A lot or unable without help = 2	
Climb stairs	How much difficulty do you have climbing a flight of 10 stairs?	None = 0 Some = 1 A lot or unable = 2	
Falls	How many times have you fallen in the past year?	None = 0 Some = 1 A lot or unable = 2	
TOTAL SCORE			

A score equal to or greater than 4 is predictive of sarcopenia and poor outcomes.

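### Adverse events form one list coded 0 = Fall to 7 = Death with no value for no event, no rule for several events, no count and no date, so numbers and rates of falls and new fractures are unreliable; separately, the falls objective has no comparator

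*Combined protocol and SAP*

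**What the plan says.** Table II (continuation) has one row for medical complications, of qualitative type, with the values "0= Fall. 1= Pneumonia. 2= New fractures. 3= Dementia. 4= Acute Myocardial Infarction 5= Pulmonary embolism. 6=Deep vein thrombosis; 7=Death". The text under Monitoring of adverse events repeats the list, introduced by "Adverse events. Catalogued in", and says that "information will be collected on variables derived from post-surgical and medical complications, and falls risk monitoring will be performed". Table III gives the instrument and timing: "Medical complications (ad hoc questionnaires) At 6 weeks, 4 months and 1 year". The annexes do not reproduce these questionnaires.

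Two other instruments touch on falls at the same three visits. SARC-F (Annex II) asks "How many times have you fallen in the past year", scored 0 for none, 1 for some and 2 for a lot. STRATIFY item 1 asks "Patient hospitalised for falls or with episodes of falls during hospitalisation".

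One specific objective is "To analyse the impact of a functional recovery programme on the prevention of falls in elderly patients" after hip fracture surgery. The introduction to the second group of variables says that these can be measured only in the unexposed (2021) cohort. The Variables section says that, before the new model, follow-up was completed at one month.

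**The concern.** An event list can support incidence figures only if three things can be told apart: the event happened, it did not happen, and nobody asked. This list provides only for the first, and gives the value 0 to a fall. It also does not say what to enter when a patient has two events, how to record a second fall, or when an event occurred.

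Fall prevention is a stated objective, and the Work plan names avoiding a second fracture among the aims of the hospital process. These are the two events that most need a clean numerator and denominator. The objective also speaks of impact, which implies a contrast, and the falls item exists in one cohort only.

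**Working it through.** The plan states no figure for falls or adverse events, so there is none to reproduce. The check compares the places where these events are recorded, then illustrates the loss under labelled assumptions.

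**1. Meaning of zero and of a blank.** Table II: 0 = fall. SARC-F falls item: 0 = none. Table III schedules both at 6 weeks, 4 months and 1 year, and clinicians, patients or relatives enter data directly in the app. A 0 entered by habit for no event becomes a fall. A blank is either no event or an unanswered item. If blanks are read as event-free, a true risk p with a blank share m (unrelated to falling) is reported as p(1 − m). With p = 25% and m = 20%, both assumed, this is 0.25 × 0.80 = 20%.

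**2. Several events at one visit.** Eight separate yes/no items allow 2^8 = 256 patterns, including none. One single-choice item allows 8, and none is not among them. The plan does not say which applies.

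**3. Repeat falls.** Assume falls follow a Poisson process with rate λ per patient-year, full follow-up and complete reporting, with at most one fall mark per window. Window lengths in years are t1 = 6/52 = 0.115, t2 = 4/12 − 6/52 = 0.218 and t3 = 8/12 = 0.667. Let q be the share of windows with a fall in which another code takes the entry.

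- Falls recorded = (1 − q) × Σ(1 − e^(−λt)).
- Patients with any fall: true 1 − e^(−λ); recorded 1 − Π[1 − (1 − q)(1 − e^(−λt))].

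For λ = 0.3, q = 0: 0.0340 + 0.0633 + 0.1813 = 0.279, and 0.279/0.3 = 93%.
For λ = 2, q = 0: 0.2061 + 0.3533 + 0.7364 = 1.296, and 1.296/2 = 65%.

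| λ (assumed) | q (assumed) | Falls recorded | Share of falls | Any fall, true | Any fall, recorded |
|---|---|---|---|---|---|
| 0.3 | 0 | 0.279 | 93% | 25.9% | 25.9% |
| 0.3 | 0.3 | 0.195 | 65% | 25.9% | 18.5% |
| 1 | 0 | 0.791 | 79% | 63.2% | 63.2% |
| 1 | 0.3 | 0.554 | 55% | 63.2% | 47.4% |
| 2 | 0 | 1.296 | 65% | 86.5% | 86.5% |
| 2 | 0.3 | 0.907 | 45% | 86.5% | 68.8% |

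The q = 0 rows also describe a form that lets several codes be ticked: the share of patients with any fall is complete, but repeat falls are lost. The q = 0.3 rows apply only if one code is allowed.

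**4. The substitutes.** SARC-F looks back one year. At 6 weeks about 52 − 6 = 46 of those weeks precede follow-up, and at 4 months about 12 − 4 = 8 months do, possibly including the fall behind the index fracture. Only the 1-year answer roughly matches follow-up, and it gives three coarse grades. STRATIFY item 1 concerns hospital-related falls and is one component of a risk score.

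**5. Dates.** A specific objective covers mortality at 30 days and one year. The first adverse-event visit is at 6 weeks, so an undated death code cannot by itself give 30-day mortality.

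**6. Comparator.** The item exists in the 2021 cohort only, and earlier follow-up stopped at one month. Better coding would not supply a 2020 fall rate over one year.

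**The case against.** The strongest reply is that the form has not been seen. The text speaks of variables in the plural and Table III of questionnaires in the plural, so the list may be a dictionary of event types with several entries per patient. That stands. A reader might infer that there is room for only one event per visit. The one-row layout, shared with plainly single-choice items such as sex and side in Table I, suggests this, but no sentence says so.

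A reader might also infer that falls, fractures and deaths cannot be counted at all. The documents do not support that. Each has its own code, so patients with a coded event can be tallied at each visit, and death occurs once. Nor is there a rule that a graver event replaces a lesser one: dementia is coded above new fracture, so the codes are not a severity ranking. The undercount at q = 0.3 is therefore conditional.

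On blanks, the other scales due at the same in-person visits would show whether the patient attended, so a missed visit can be separated from an attended one. The ambiguity is confined to an unanswered item at an attended visit, and the 25% to 20% example is an upper-end illustration. SARC-F at 1 year does give an any-fall proportion with an explicit none answer.

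Under every reading, there is still no value for none or not assessed, no count, no date, and two opposite meanings of zero.

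**Conclusion.** The point holds in a bounded form. As specified, numbers and rates of falls and new fractures cannot be derived reliably, while patients with at least one coded event can be tallied, with undercounting if only one code is allowed. Over the assumed range of 0.3 to 2 falls per patient-year, between 7% and 35% of falls are lost to repeats alone; with an assumed 30% displacement, 35% to 55% are lost. The documents give no fall rate, so these figures show scale and are not estimates for this cohort.

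A reader might conclude that the coding is what prevents the falls objective from being answered. It is not the main cause. The objective cannot show a preventive effect because there is no comparator, and that would remain with perfect coding. The two matters need separate corrections.

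**What to change.** - Replace the single code list with one field per event (yes / no / not assessed) and an event date, at 6 weeks, 4 months and 1 year. Add the number of falls since the last contact. If the questionnaires already work this way, reproduce them in an annex and correct Table II to match.
- Name reported falls, not the STRATIFY score, as the measure for the falls objective.
- Reword that objective as describing fall incidence in the 2021 cohort. Make no between-year comparison of falls or new fractures unless the 2020 records are shown to hold the same event, ascertained the same way over the same period. Nothing in the documents shows that they do.

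The cost is a slightly longer form, one changed sentence in the objectives, and a more modest claim about falls.

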This programme is divided into 5 phases, each of these phases coincides with a level of the gait assessment scale. Each individual will start at the level assigned by the doctor and will only have access to the videos of the indicated level and the levels below it. As the patient meets the recovery goals, the physician will provide access to the higher level videos. The functional recovery plan begins the day after the hip fracture and continues after the patient has been discharged for a total of 16 weeks.

- The therapeutic plan for the historical control group (standard practice until 31 December 2020) consisting of postural changes described in the standardised nursing care plan. Within this plan, the patient was moved to a sitting position prematurely (within the first 24 hours) and started to ambulate within the following 48

hours, provided that the patient's general condition allowed it. This group did not receive any specific functional recovery plan.

- The patient is discharged from hospital and will be assigned a link where he/she will be able to access the online platform to send information from the questionnaires sent during the established periods of 1, 3, 6 and 12 months and will also be sent videos illustrating the rehabilitation exercises that he/she will have to perform during this period. The patient and/or carer will be explained how the tool works, how to access the digital information content and how to access the questionnaires. A means of contact will be provided to resolve doubts, if any. The PI will have access through the web/app platform to a control panel where he/she will be able to detect a patient's lack of adherence, if any, or alerts related to clinical evolution, allowing for exhaustive monitoring of the patient.
- Analysis of results: The data collected will be analysed with the SPSS programme. The mean, median and standard deviation of each of the variables will be calculated. Based on the data obtained from the existing literature(31), having selected a sample of 67 patients, a normal distribution can be assumed for all variables  
For baseline demographic and clinical characteristics, a comparison of means for quantitative variables (t-Student), and of proportions (Chi-square) for qualitative will be performed  
The statistical analysis will be carried out with a confidence level of 95%, so that statistically significant values will be considered to be those whose probability is < 0.05.

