### **Sit / stand up**

Sit on the edge of the chair with your cushion raised. Lifts from the chair and sit back several times. First begin to do it with the operated leg in front and as you are able to flex the leg more, slow down your position. Don't bend your hips more than 90 degrees. Repeat 8 to 15 times.

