## **RECOMMENDATIONS**

### **Do not cross your legs**

You should not sit in low chairs for a long time, or stay cross-legged.

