### **Do not rotate the hips when loaded**

The hips should not remain rotated. Remember that your toes and knee should point forward.

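### Post-surgical complications are promised, but none of the eight adverse-event codes is specific to the operated hip, implant or wound, and there is no 'other' code

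*Combined protocol and SAP*

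**What the plan says.** The section on monitoring of adverse events (Variables, second group) sets the scope: during follow-up, "information will be collected on variables derived from post-surgical and medical complications". Directly below, under "Adverse events. Catalogued in", it gives a numbered list from 0 to 7, to be completed at 6 weeks, 4 months and 1 year. Table II (continuation) repeats the list in a row labelled as medical complications: "0= Fall. 1= Pneumonia. 2= New fractures. 3= Dementia. 4= Acute Myocardial Infarction 5= Pulmonary embolism. 6=Deep vein thrombosis; 7=Death". In Table III the matching entry begins "Medical complications (ad hoc questionnaires", with the same three time points. Neither table has a row for surgical complications.

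The text introducing the second group of variables says that they can be measured only in the 2021 cohort.

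The programme under study includes standing, stair and strength exercises and, according to the description of the process, "continues after the patient has been discharged for a total of 16 weeks". Its text in Annex VIII contains hip-position warnings: "Don't bend your hips more than 90 degrees" (Level 5, sit / stand up), "You should not sit in low chairs for a long time, or stay cross-legged" and "The hips should not remain rotated" (both under Recommendations).

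The eligibility section also lists complications, without defining them, as a reason for withdrawal from the 2021 cohort.

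**The concern.** The scope sentence names two classes of complication, and the variable definitions appear to serve only one. If a patient's fixation fails, hip dislocates or wound becomes infected, a site following the code list has no value that describes the event.

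Two things depend on this. First, these are local harms that a reader would look for in a study of an exercise programme done largely after discharge, and the programme's own warnings show that its authors had hip position in mind. Second, one specific objective is to analyse risk and protective factors for dependency and mortality at 30 days and one year. A reoperation or failed fixation is an obvious candidate factor for dependency, and it is not a defined variable.

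**Working it through.** The plan states no figure on this point. The check is a count of codes and a search for any other place where such an event could be recorded.

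**Step 1. Classify the eight codes.**

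| Code | Event | Specific to operated hip, implant or wound? | Could it be post-surgical? |
|---|---|---|---|
| 0 | Fall | No | Not as such |
| 1 | Pneumonia | No | Yes, as a general complication |
| 2 | New fractures | No; site not stated | Yes, if at the operated hip |
| 3 | Dementia | No | Not as such |
| 4 | Myocardial infarction | No | Can follow surgery, but coded as medical |
| 5 | Pulmonary embolism | No | Yes |
| 6 | Deep vein thrombosis | No | Yes |
| 7 | Death | No | Cause not coded |

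Codes specific to the hip, implant or wound: 0 of 8. Open or 'other' codes: 0 of 8. Code 2 can hold a fracture at the operated hip, but does not separate it from a fracture elsewhere.

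**Step 2. Compare the places that define the data.** The scope sentence names post-surgical and medical complications. The list below it has no local surgical item, Table II has the same codes under a medical label, and Table III schedules only a medical item. The local surgical part of the scope has no variable in any of the three.

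**Step 3. Look for another route.**

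- *App questionnaires.* The data collection procedure says that the tool's questionnaires are those in Table III, which has no surgical entry.
- *App alerts.* They are generated from the data collected, so they add no event field.
- *Routine-practice data.* The procedure says in general terms that routine variables pass through the app, but it names no surgical event. Extraction is of the variables established for this study.
- *Oxford Hip Score (Annex III).* It covers hip pain, including sudden severe pain, limping and function, at 1, 3, 6 and 12 months. These are symptoms. A low score does not distinguish slow recovery from a dislocation or a reoperation.
- *Withdrawal for complications.* The type of complication is not defined and no field for it is described.

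None of these routes defines or codes a surgical hip event.

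**Step 4. Comparison between cohorts.** Follow-up adverse events are planned for 2021 only. The Variables section says that follow-up and data collection previously ended after one month. As planned, there is no one-year counterpart for 2020.

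**The case against.** The strongest reply is that the list is less bare than it looks. New fractures has no site limit, and embolism, thrombosis and pneumonia can all follow hip surgery. Nothing says which codes serve which class, so some post-surgical events do have a home. That stands, and it limits the point to local events of the hip, implant and wound.

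Second, the trauma team sees patients at scheduled visits, routine data enter the app, the ad hoc questionnaires are not reproduced, and the database is adapted from registry forms that the documents do not show. A reader might infer from the code list that such events would never be recorded. The documents do not support that: an event could be noted in the chart or on an unseen form. They show only that no code is defined for it, and Table II gives the values of this item as 0 to 7.

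Third, a reader might infer that a reoperated patient would be analysed as someone whom the programme failed. The withdrawal criterion for complications means that the patient may instead leave the cohort, so the direction of any bias cannot be read from the text.

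Fourth, the objectives promise no benefit-risk conclusion, the programme is already standard practice, and the confidentiality section limits collection to what is strictly necessary. The first two are fair, and this point does not claim that a stated safety objective fails. The third does not exclude the added codes, because the scope sentence already includes post-surgical complications.

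Finally, a comparison with 2020 is harder than it sounds. It needs new record review beyond one month. Patients are referred from another centre's emergency department, so events treated elsewhere may be missed. This stands and is carried into the fix.

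**Conclusion.** The mismatch is real, and narrow. The plan commits to collecting post-surgical complications, but 0 of its 8 codes is specific to the operated hip, implant or wound and none is open-ended. Dislocation, fixation or implant failure, wound or deep infection, reoperation and readmission cannot be reliably counted as adverse events under the plan as written.

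This rests on reading Tables II and III as the full definition of the item. If the unreproduced questionnaires already hold such fields, the remaining task is to bring the protocol text into line with them.

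No number of affected patients can be given. The documents state no rate for these events. The figure of 67 appears only in a remark about assuming normality, whereas the sampling section includes the whole cohort. The gap does not by itself invalidate the functional comparison. It is a harms-capture weakness that is cheap to close.

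**What to change.** Make the code list match the stated scope, in the adverse-event section and in Tables II and III:

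- Add dislocation; fixation or implant failure; wound or deep infection; reoperation on the index hip; unplanned readmission; and 'other (specify)'. Record a date for each.
- Collect them at the existing 6-week, 4-month and 1-year visits.
- For any patient withdrawn because of complications, record the event and its date. The withdrawal criterion and the adverse-event section must be reconciled so that the two use the same definition of a complication.
- Where the hospital record allows, extract reoperation and readmission for both the 2020 and 2021 cohorts from that one source. State in the report that events treated elsewhere may be missed.

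A field for whether an event happened during an exercise is not recommended as a comparative variable. It would depend on recall between widely spaced visits and has no meaning for 2020 patients, who had no programme.

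The cost is six added codes with dates on a form already in use, slightly more data entry, and a limited record look-up. The look-up is the larger part, because for 2020 it goes beyond the one-month follow-up. No new visits or procedures are needed.

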**Annex IV. Questionnaire EQ-5D-5L for quality of life**

**Mobility**

I have no problems in walking about

I have some problems in walking about

I am confined to bed

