**Self-Care**

I have no problems with self-care

I have some problems washing or dressing myself

I am unable to wash or dress myself

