**Usual Activities (e.g. work, study, housework, family or leisure activities)**

I have no problems with performing my usual activities

I have some problems with performing my usual activities

I am unable to perform my usual activities

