**Pain/Discomfort**

I have no pain or discomfort

I have moderate pain or discomfort

I have extreme pain or discomfort

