**Anxiety/Depression**

I am not anxious or depressed

I am moderately anxious or depressed

[figure not shown]
I am extremely anxious or depressed

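### Annex IV, labelled EQ-5D-5L, prints three answers per dimension where the text specifies five levels and 3125 states; the version loaded in the app must be confirmed

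*Combined protocol and SAP*

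**What the plan says.** The Variables section introduces the instrument as "EQ-5D-5L questionnaire (ANNEX IV", so Annex IV is the form to which the text refers. The description that follows states: "Each of these dimensions has five possible responses or severity levels". It keys them from 1 (no problems) through mild, moderate and severe to 5 (extreme or impossible), sets 11111 as the best profile and 55555 as the worst, and counts 3125 states. Table II (continuation) repeats the count in its unit column: "Levels (1 to 3125". Table III schedules the EQ-5D-5L at months 1, 3, 6 and 12.

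Annex IV is also headed EQ-5D-5L, on both of its parts. Every dimension on it has one answer for no difficulty, one middle answer and one worst answer. The middle answer for mobility, for example, is "I have some problems in walking about", and for pain it is "I have moderate pain or discomfort".

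The Data collection procedure says the information is gathered through a mobile application, completed from home by the patient or main caregiver. The application's questionnaire screens are not shown.

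**The concern.** A form with three answers cannot produce a code running from 1 to 5, and nothing in the protocol maps one to the other. If the app follows the annex, patients with mild or severe problems have no answer that says so. The five-digit profiles described in the text could then not be obtained at any of the four time points.

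Describing quality of life and patient-reported outcomes in the 2021 cohort is one of the Specific objectives. A level that was never offered cannot be recovered afterwards, so the version needs to be settled before answers are collected, or at the latest before they are analysed.

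**Working it through.** **Inputs.** From the quality-of-life item in the Variables section: 5 dimensions, 5 levels each, 3125 states. From Annex IV, by counting the printed answers:

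| Dimension | Best answer | Middle answer | Worst answer | Printed |
|---|---|---|---|---|
| Mobility | no problems | "I have some problems in walking about" | confined to bed | 3 |
| Self-care | no problems | "I have some problems washing or dressing myself" | unable | 3 |
| Usual activities | no problems | "I have some problems with performing my usual activities" | unable | 3 |
| Pain/discomfort | none | "I have moderate pain or discomfort" | extreme | 3 |
| Anxiety/depression | none | "I am moderately anxious or depressed" | extreme | 3 |

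**1. The plan's own figure.** States = levels^dimensions = 5^5 = 3125. This reproduces the number in the text and in Table II.

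**2. The printed form.** 3^5 = 243 states, and 243 / 3125 = 7.8% of the stated count. Coded in its own order, its worst profile would be 33333, not 55555.

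**3. Levels without an answer.** (5 − 3) × 5 = 10 of the 5 × 5 = 25 planned levels. This holds however the three answers are mapped, because three answers can fill at most three levels.

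**4. Whether the 1–5 code could be reconstructed.** For pain and anxiety, the middle wording matches level 3, so levels 2 and 4 are empty. For the other three dimensions, the middle answer speaks only of some problems, which is the name of none of levels 2, 3 or 4. Assume that *moderate* is level 3 and that *some problems* could be any of levels 2 to 4. A patient who gives the middle answer throughout then fits 3 × 3 × 3 × 1 × 1 = 27 five-level profiles, from 22233 to 44433. The plan has no rule for choosing among them.

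**5. Could the missing answers have been lost when the PDF was read?** This is unlikely. Exactly two answers would have had to disappear from each of five dimensions, and only one dimension (anxiety/depression) has a missing-figure marker. Annex III, the Oxford Hip Score, is also a five-option form, and all 12 of its items came through with five options.

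**6. What agrees.** The visual analogue scale runs from 0 to 100 in both the text and Annex IV.

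**The case against.** The strongest reply is that only the annex is wrong. Table II, the descriptive text and Table III all name the five-level instrument, and the text defines it in detail. The Data collection procedure says the app carries the questionnaires listed in Table III. The annexes also look like English reproductions rather than the forms used in León: Annexes I and II are described as Spanish versions yet print English text with distances in yards and weights in pounds. On that reading, patients already see five answers.

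This may well be so, but the documents do not establish it. The name EQ-5D-5L in Table III does not settle the version, because the three-answer form in Annex IV carries the same name. Annex IV is the only form shown.

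A second reply concerns weight. The objective is descriptive and covers one cohort. The analysis paragraph of the Work plan specifies summary statistics and baseline comparisons, with no utility index, no change score and no between-cohort test on this questionnaire. That stands, and it limits the worst case to a coarser profile for one secondary outcome. The counts of 243 and 27 express the mismatch between three answers and five; they do not measure bias, and the 27 depends on an assumed reading of the middle answers.

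**Conclusion.** The concern holds. The text and the form it cites contradict each other in all five dimensions, and the form as printed cannot yield the codes that the plan states. If that form, or app screens matching it, is used, 10 of the 25 planned levels cannot be recorded and 243 states replace 3125. If the app already offers five answers, the error is confined to the annex.

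The first outcome depends on an app version that the documents leave open. In either case, the visual analogue scale, the overall functional-recovery objective and every comparison between the 2020 and 2021 cohorts are unaffected. This should be corrected, but it does not threaten the main result.

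**What to change.** Confirm which version the app carries, and then:

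- **Five answers in the app:** replace Annex IV with the five-option form.
- **Three answers in the app, no data yet:** change both the app and Annex IV to the five-option form before collection starts.
- **Three-level answers already collected:** restate the instrument name, the levels (1 to 3), the profile range (11111 to 33333) and the state count (243) in Table II, the descriptive text, Table III and Annex IV. Do not report those answers on the 1–5 key.

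The cost is a configuration check and a form swap in the annex. The documents give no cost for changing the app. Levels not offered in data already gathered are lost, so those data would support only the three-level profile.
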